### **10.3.3.3 Assessment of Liver Elevations**

The frequencies and percentages of subjects with post baseline liver-specific function test values that meet the criteria of potential clinical interest (as described in Section 10.3.2.4) will be summarized by the actual treatment received at the time of the event occurrence. Starting with Amendment 6, all subjects will receive open-label upadacitinib 15 mg QD, including those currently on upadacitinib 30 QD. The treatment exposure groups for summarizing liver elevations are the same as the ones for long-term AE analysis as described in Section 8.1 and Section 10.2.2.

A subject can be counted under different treatment groups if he/she switched treatment and experienced potentially clinical significant laboratory values under different treatment groups.

A listing of potentially clinically significant liver elevations based on criteria specified above will be provided. For each of these subjects, the whole course of the respective parameter will be listed.

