#### **Long-Term Safety Analysis**

Long-term safety analyses that account for protocol-defined treatment switching include reporting of AE rate adjusted by cumulative exposure, mean change from baseline in laboratory parameters and vital sign variables, and rate of potentially clinically significant laboratory and vital signs values. The treatment-emergent adverse event (TEAE) rate per 100 patient-years of exposure will be presented by actual treatment received at the time of

AE (as described in Section 10.2.2). Listing of subjects with TEAEs by SOC and PT will be provided. Mean changes from baseline in all continuous laboratory parameters and vital signs variables at each visit will be summarized by "as treated" treatment group sequences defined as follows (as described in Section 10.3.3 and Section 10.4.3). Frequency tables and listings of subjects meeting criteria for potentially clinically significant vital sign values and for potentially clinically significant laboratory values will be provided by actual treatment received at the time of event. Missing safety data will not be imputed.

"As treated" treatment group sequences:

1. Upadacitinib 15 mg QD
2. Upadacitinib 30 mg QD
3. Placebo → Upadacitinib 15 mg QD
4. Placebo → Upadacitinib 30 mg QD

Starting with Amendment 6, all subjects will receive open-label upadacitinib 15 mg QD, including those currently on upadacitinib 30 mg QD. For subjects who previously received upadacitinib 30 mg QD, adverse events and exposure to upadacitinib 30 mg QD will be censored at the time of dose switch; subsequent adverse events and exposure starting the day of first dose of upadacitinib 15 mg QD will be summarized under a separate group, as defined in Section 8.1. Assessment of potentially clinical significant laboratory and vital sign values will be based on the same treatment exposure groups as for adverse events, as described above. For summary of mean change from baseline in laboratory values and vital signs, exposure sequences 2 and 4 (i.e., subjects who switched from upadacitinib 30 mg QD to 15 mg QD) will be censored at the time of dose switch. Mean change from baseline for laboratory values and vital signs collected after dose switch will be summarized separately by visits post switch.

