### **10.3.3.2 Assessment of Potentially Clinical Significant Laboratory Values**

Long-term laboratory data will be summarized based on the number and percentage of subjects meeting the criteria for potentially clinical significant laboratory values and by the actual treatment received at the time of the event occurrence. Starting with Amendment 6, all subjects will receive open-label upadacitinib 15 mg QD, including those currently on upadacitinib 30 QD. The treatment groups for summarizing potentially clinical significant laboratory values are the same as the ones for long-term AE analysis as described in Section 8.1 and Section 10.2.2. A subject can be counted under different treatment groups if he/she switched treatment and experienced potentially clinical significant laboratory values under different treatment groups.

In the evaluation of potentially clinically significant laboratory values, the baseline value will be determined by the last non-missing measurement recorded on or before the date of the first dose of study drug in the corresponding treatment group (which may be different than the first dose of study drug received in the study). For example, for a subject who started on Placebo and switched to upadacitinib 15 mg QD, lab values under upadacitinib 15 mg QD exposure would be evaluated against the baseline value defined as the last non-missing measurement recorded on or before the date of the first dose of upadacitinib 15 mg QD. For subjects who switched from upadacitinib 30 mg QD to upadacitinib 15 mg QD, lab values under upadacitinib 15 mg QD exposure would still be evaluated against the baseline defined based on the first dose of upadacitinib 30 mg QD.

A listing of all subjects with any laboratory determination meeting OMERACT criteria of Grade 3 or 4 will be provided by Grade. For creatine phosphokinase and creatinine, NCI CTC criteria will be used. For each of these subjects, the whole course of the respective parameter will be listed.

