#### 10.4.3 Analysis of Long-Term Vital Sign

Analyses of mean change from baseline in continuous vital signs variables which are measured longitudinally will be performed by visits and by "as treated" treatment group sequences as described in Section 10.1. For each change from baseline analysis, the following summary statistics will be presented for each treatment group: sample size, baseline mean, visit mean, and the mean, standard deviation, and median of the changes from baseline.

Long-Term Vital Sign will also be summarized based on the number and percentage of subjects meeting the criteria for potentially clinical significant vital sign values and by the actual treatment received at the time of the event occurrence. The treatment groups are the same as the ones for long-term AE analysis as described in Section 8.1 and Section 10.2.2. A subject can be counted under different treatment groups if he/she switched treatment and experienced potentially clinical significant laboratory values under different treatment groups.

In the evaluation of potentially clinically significant vital sign values, the baseline value will be determined by the last non-missing measurement recorded on or before the date of the first dose of study drug in the corresponding treatment group, similarly as described in Section 10.3.3.2.

Starting with Amendment 6, all subjects will receive open-label upadacitinib 15 mg QD, including those currently on upadacitinib 30 QD. Mean change from baseline in vital signs for subjects who switched from upadacitinib 30 mg QD to 15 mg QD will be censored at the time of dose switch, and mean change from baseline for values post switch will be summarized separately, similarly as described in Section 10.3.3.1. The treatment groups for summarizing potentially clinical significant vital sign values are the same as the ones for long-term AE analysis as described in Section 9.1 And Section 10.2.2. For the purpose of evaluating potentially clinical significant vital sign values, for subjects who switched from upadacitinib 30 mg QD to upadacitinib 15 mg QD, baseline is defined based on the first dose of upadacitinib 30 mg QD, similarly as described in Section 10.3.3.2.

A listing of all subjects with any vital sign values meeting the criteria for potentially clinically significant vital signs will be provided. For each of these subjects, the whole course of the respective parameter will be listed.

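### Long-term laboratory, liver and vital-sign abnormalities are shown as crude percentages across groups with planned exposure from 12 to 260 weeks, so the percentages are confounded with time on treatment

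*SAP*

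**What the plan says.** Three long-term safety summaries use the same measure:

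- **Laboratory values, SAP 10.3.3.2:** "Long-term laboratory data will be summarized based on the number and percentage of subjects meeting the criteria for potentially clinical significant laboratory values".
- **Liver elevations, SAP 10.3.3.3:** "The frequencies and percentages of subjects with post baseline liver-specific function test values" meeting the listed criteria. These "will be summarized by the actual treatment received at the time of the event occurrence".
- **Vital signs, SAP 10.4.3:** "Long-Term Vital Sign will also be summarized based on the number and percentage of subjects meeting the criteria".

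The groups are shared with the adverse-event analysis: "The treatment exposure groups for summarizing liver elevations are the same as the ones for long-term AE analysis". SAP 8.1 defines four of them: placebo; 15 mg, including subjects who moved from placebo; 30 mg, also including former placebo subjects and censored at the dose switch; and 15 mg after 30 mg. SAP 7.0 notes that the visit at which the switch happens can vary between subjects.

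SAP 10.1 says the long-term analyses "include reporting of AE rate adjusted by cumulative exposure", and SAP 10.2.2 puts the events over patient-years. The same sentence of 10.1 uses the word rate for the laboratory and vital-sign findings. It does not attach the exposure adjustment to them, and it goes on to specify frequency tables. None of the three sections gives a person-time denominator, a time-to-event method or a common time point for these percentages.

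**The concern.** A subject enters the numerator with one qualifying value. The percentage therefore grows with time on treatment and with the number of tests, whatever the drug does. The four groups differ greatly in both. From Protocol Tables 2 and 4, a placebo subject has 4 scheduled post-baseline visits with safety laboratory tests and vital signs (Weeks 2, 4, 8 and 12). A subject on 15 mg from the start has 26.

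A reader who sees these percentages side by side will compare them. Placebo would look much cleaner than either dose even with no drug effect, and 30 mg would look better relative to 15 mg than it is. Evaluating the long-term safety of both doses is the Period 2 objective. The same report would give hepatic and CPK adverse events per 100 patient-years next to ALT and CPK values as unadjusted percentages of the same groups.

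**Working it through.** **Inputs from the documents**

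- Treatment duration: 12 weeks in Period 1 and 248 weeks in Period 2 (Protocol Synopsis).
- Group sizes: 200 on 15 mg, 200 on 30 mg and 200 on placebo, of whom 100 move to each dose (Protocol 5.1).
- Groups: SAP 8.1.

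**Assumptions, because the documents give no figures**

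- A constant first-event rate, varied from 1 to 20 per 100 patient-years (PY).
- 30 mg exposure of 2 to 4 years before the switch.
- No dropout, except where stated.

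**Step 1. The plan's own duration.** 12 + 248 = 260 weeks, which agrees with the protocol. In years, 260 × 7/365.25 = 4.98, 248 × 7/365.25 = 4.75 and 12 × 7/365.25 = 0.23. The ratio at the extremes is 260/12 = 21.7. Mean planned exposure in the 15 mg group is (200 × 260 + 100 × 248)/300 = 256 weeks, or 4.91 years, which is 21.3 times placebo. The plan states no figure for the percentages themselves.

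**Step 2. Formula.** The expected share of subjects with at least one qualifying value is 1 − exp(−rate × years).

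**Step 3. Placebo versus 15 mg with the same true rate.** At 2 per 100 PY:

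- Placebo: 1 − exp(−0.02 × 0.23) = 0.46%.
- 15 mg: the 200:100 weighted mean of 1 − exp(−0.02 × 4.98) and 1 − exp(−0.02 × 4.75) = 9.3%.

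| Rate per 100 PY | Placebo | 15 mg | Ratio | 15 mg, 60% of planned exposure | Ratio | Ratio if 15 mg halves the rate (full exposure) |
|---|---|---|---|---|---|---|
| 1 | 0.23% | 4.8% | 20.8 | 2.9% | 12.6 | 10.5 |
| 2 | 0.46% | 9.3% | 20.4 | 5.7% | 12.5 | 10.4 |
| 5 | 1.14% | 21.8% | 19.0 | 13.7% | 12.0 | 10.1 |
| 10 | 2.27% | 38.8% | 17.1 | 25.5% | 11.2 | 9.6 |
| 20 | 4.50% | 62.5% | 13.9 | 44.5% | 9.9 | 8.6 |

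**Step 4. Between active groups, 2 per 100 PY in all of them (15 mg shows 9.3%).** The 30 mg figure is 1 − exp(−0.02 × c) for a switch after c years. The switched group has 4.98 − c years for a subject who began on 30 mg. The two percentages are equal when rate(30 mg) × c = rate(15 mg) × 4.91, so the break-even rate ratio is 4.91/c.

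| Switch after | 30 mg | 15 mg after 30 mg | True 30 mg : 15 mg rate ratio at which the percentages are equal |
|---|---|---|---|
| 2 years | 3.9% | 5.8% | 2.45 |
| 3 years | 5.8% | 3.9% | 1.64 |
| 4 years | 7.7% | 1.9% | 1.23 |

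A true 30 mg excess below the last column would appear as no excess, or as a deficit. For example, 3 per 100 PY on 30 mg over 2.5 years gives 1 − exp(−0.075) = 7.2%, below the 9.3% for 15 mg at 2 per 100 PY.

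**Step 5. With person-time.** Planned exposure is 200 × 12 weeks = 46 PY on placebo and (200 × 260 + 100 × 248) weeks = 1,472 PY on 15 mg. First-event rates over time at risk would be the same in expectation, 2.0 per 100 PY in both groups, when the true rates are equal.

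**The case against.** The strongest reply is that these tables are descriptive and that the controlled comparison is made elsewhere. Much of this is correct:

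- **No inference.** No test, difference or interval is planned for the long-term percentages. Where the SAP wants a long-term contrast with placebo (10.2.2.1, adverse events of special interest), it uses exposure-adjusted rates.
- **Period 1.** Sections 10.3.2.3, 10.3.2.4 and 10.4.2 give the same kinds of finding over the same planned 12 weeks, with Fisher's exact test for laboratory values.
- **Other long-term outputs.** Hepatic disorder, CPK elevation, anemia, neutropenia, lymphopenia and renal dysfunction are reported per 100 PY as adverse events of special interest. Exposure is summarised for the same groups, and mean changes are given by visit.

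This limits the point without removing it. Period 1 says nothing about the period after Week 12. Under Protocol 6.1.1.1 a laboratory abnormality becomes an adverse event only in certain circumstances, so the adverse-event rates cover these values in part. An exposure table does not show time at risk to a first qualifying value.

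Three stronger readings are tempting, and the documents do not support them:

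- **That time on treatment is the main driver of every contrast in these tables.** The calculation shows this for placebo against active treatment under a constant rate. Between doses the displayed ratio is about 1.2 to 2.4 on the assumed switch times. If first abnormalities cluster early in treatment, the bias shrinks.
- **That a 30 mg excess would necessarily be masked.** With a switch at 3.5 years, a doubled rate gives 1 − exp(−0.04 × 3.5) = 13.1% against 9.3%, which is visible. The outcome depends on switch timing, which is not given.
- **That these tables are the Hy's Law screen.** That purpose is stated in 10.3.2.4, for Period 1. In the long term, 10.3.3.3 lists every qualifying subject with the full course of the parameter, so finding cases does not depend on the percentages.

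**Conclusion.** The point holds as a reporting defect in three descriptive long-term safety summaries. It does not affect the efficacy results or the Period 1 safety comparisons. The percentages are confounded with time on treatment, and the SAP already adjusts adverse events in the same groups for exposure.

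Against placebo, equal true rates would appear as about a 14- to 21-fold difference at full planned exposure, and about 10- to 13-fold at 60% of it. Between doses the distortion is material but smaller, and it works against detecting a modest 30 mg excess. These sizes rest on an assumed constant first-event rate and on assumed switch times. The direction of the bias rests only on the unequal exposure and on counting a subject from one qualifying value.

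**What to change.** In SAP 10.3.3.2, 10.3.3.3 and 10.4.3, add for each Section 8.1 group the number of subjects with a first qualifying value per 100 patient-years at risk, with a 95% CI. Person-time should stop at the first qualifying value, the dose switch or the end of exposure. Keep n and % as descriptive columns, and align the wording of 10.1 with this.

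State the at-risk rule within each group. In particular, say whether a subject who already qualified on 30 mg is at risk again after the switch. For laboratory and vital-sign findings, the SAP keeps that subject's baseline tied to the first 30 mg dose, so the same abnormality could be counted again on 15 mg.

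The cost is modest. The exposure data already exist for the adverse-event rates, but time to first qualifying value must be derived for each parameter. SAP 11.1 says this version governs only future long-term reporting, so completed Period 1 results are untouched.

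Some limits remain. The rates summarise well only if the hazard is roughly constant. They also still depend on visit frequency: visits are closer together in Period 1 than the mostly 12-weekly visits later. The placebo rate will be imprecise: 46 PY × 0.02 gives about 0.9 expected events at 2 per 100 PY. The interval would show that.

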## **10.4 Analysis of Vital Signs**

### **10.4.1 Variables and Criteria Defining Abnormality**

Vital sign variables include sitting systolic blood pressure, sitting diastolic blood pressure, pulse rate, respiratory rate, body temperature, and weight. The criteria for potentially clinically significant vital sign findings are presented in Table 10.

**Table 10. Criteria for Potentially Clinically Significant Vital Sign Findings**

Vital Sign	Category	Criteria for Potential Clinically Significant Vital Signs
Systolic blood pressure	Low	Value $\leq$ 90 mmHg and decrease $\geq$ 20 mmHg from Baseline
	High	Value $\geq$ 160 mmHg and increase $\geq$ 20 mmHg from Baseline
Diastolic blood pressure	Low	Value $\leq$ 50 mmHg and decrease $\geq$ 15 mmHg from Baseline
	High	Value $\geq$ 105 mmHg and increase $\geq$ 15 mmHg from Baseline
Weight	High	> 7% increase from baseline
	Low	> 7% decrease from baseline

#### 10.4.2 Analysis of Vital Sign for Period 1

Analyses of mean change from baseline in continuous vital sign variables which are measured longitudinally will be performed by visits and by the "as treated" treatment groups of upadacitinib 15 mg QD, upadacitinib 30 mg QD, and combined placebo groups. For each change from baseline analysis, the following summary statistics will be presented for each treatment group: sample size, baseline mean, visit mean, and the mean, standard deviation, and median of the changes from baseline. An ANOVA model with treatment as factor, will be used to test statistical significance for the change from baseline mean among different treatment groups.

The number and percentage of subjects meeting the criteria for potentially clinically significant vital sign values will be summarized by "as treated" treatment group and overall.

#### 10.4.3 Analysis of Long-Term Vital Sign

Analyses of mean change from baseline in continuous vital signs variables which are measured longitudinally will be performed by visits and by "as treated" treatment group sequences as described in Section 10.1. For each change from baseline analysis, the following summary statistics will be presented for each treatment group: sample size, baseline mean, visit mean, and the mean, standard deviation, and median of the changes from baseline.

Long-Term Vital Sign will also be summarized based on the number and percentage of subjects meeting the criteria for potentially clinical significant vital sign values and by the actual treatment received at the time of the event occurrence. The treatment groups are the same as the ones for long-term AE analysis as described in Section 8.1 and Section 10.2.2. A subject can be counted under different treatment groups if he/she switched treatment and experienced potentially clinical significant laboratory values under different treatment groups.

In the evaluation of potentially clinically significant vital sign values, the baseline value will be determined by the last non-missing measurement recorded on or before the date of the first dose of study drug in the corresponding treatment group, similarly as described in Section 10.3.3.2.

Starting with Amendment 6, all subjects will receive open-label upadacitinib 15 mg QD, including those currently on upadacitinib 30 QD. Mean change from baseline in vital signs for subjects who switched from upadacitinib 30 mg QD to 15 mg QD will be censored at the time of dose switch, and mean change from baseline for values post switch will be summarized separately, similarly as described in Section 10.3.3.1. The treatment groups for summarizing potentially clinical significant vital sign values are the same as the ones for long-term AE analysis as described in Section 9.1 And Section 10.2.2. For the purpose of evaluating potentially clinical significant vital sign values, for subjects who switched from upadacitinib 30 mg QD to upadacitinib 15 mg QD, baseline is defined based on the first dose of upadacitinib 30 mg QD, similarly as described in Section 10.3.3.2.

A listing of all subjects with any vital sign values meeting the criteria for potentially clinically significant vital signs will be provided. For each of these subjects, the whole course of the respective parameter will be listed.

## 11.0 Summary of Changes

### 11.1 Summary of Changes between the Previous Version and the Current Version

The primary efficacy analysis and Period 1 reporting have been completed under the SAP version 2.0. The current SAP update applies only to future reporting of long-term analysis.

1. Updated throughout the SAP to align with Protocol Amendment 6, 7, and 8 including handling of dose switch from upadacitinib 30 mg QD to 15 mg QD (hereafter referred to as "dose switch") and change of study length from up to 5 years to 260 weeks. Updated throughout the SAP to replace "ABT-494" with "upadacitinib."
2. Updated Section 7.0. To clarify analysis details and incorporate additional summary of dose switch.
3. Updated Section 8.1. Study drug exposure groups to accommodate dose switch.
4. Updated Section 9.1.1 and Section 9.3. To incorporate handling of dose switch for long-term efficacy analysis.
5. Updated Section 9.1.2. To describe the missing data handling approach for the additional sensitivity analysis using longitudinal models for long-term efficacy.
6. Updated Section 9.3. To incorporate the additional sensitivity analysis for long-term efficacy.
7. Added language to clarify analysis details in Section 10.2.1.1, Section 10.2.1.6, Section 10.2.2.1, Section 10.2.2.3, Section 10.3.3.2, and Section 10.4.3.
8. Updated Section 10.2.1.6, and Section 10.4.1. To align with the latest upadacitinib AESI definitions in PSSAP V4.0.

9. Updated Section 10.1., Section 10.2.2, Section 10.3.3.1 Section 10.3.3.2 Section 10.3.3.3 and Section 10.4.3 to incorporate handling of dose switch for long-term safety analysis.
10. Added Appendix B to describe analysis accounting for impact of COVID-19 pandemic.
11. Added Section 11.0 for summary of changes and Section 12.0 for SAP version history summary.

## 12.0 Version History

**Table 11. SAP Version History Summary**

Version	Date	Summary
1.0	27 Dec 2016	Original version (submitted to FDA to gain feedback).
2.0	14 Apr 2017	Updated to incorporate FDA feedback. Version 2.0 was used for the primary analysis.
3.0	17 Dec 2020	Updated to align with Protocol Amendment 6, 7, and 8 including handling of dose switch from upadacitinib 30 mg QD to 15 mg QD. Included additional sensitivity analysis for long-term efficacy, and analyses due to COVID-19 impact.

## 13.0 Appendix

[Appendix A](#)

OMERACT Criteria

[Appendix B](#)

Statistical Analysis to Account for Impact of COVID-19 Pandemic

